3.7.2 Other Secondary Endpoints, North America and Europe

The other secondary endpoints are as follows:

- Maximum dose achieved with no or mild symptoms at Exit DBPCFC in subjects aged 4 to 17 years
- Change from baseline in maximum tolerated dose of peanut protein at DBPCFC in subjects aged 4 to 17 years
- Use of epinephrine as a rescue medication at Exit DBPCFC and comparison to its use at Screening DBPCFC in subjects aged 4 to 17 years
- Changes in peanut-specific serum IgE and IgG4 levels in subjects aged 4 to 17 years
- Changes in peanut skin prick test (SPT) mean wheal diameters in subjects aged 4 to 17 years
- Quality of life assessments using the food allergy related quality of life questionnaire (FAQLQ), and the food allergy independent measure (FAIM) questionnaire (van der Velde et al., 2010) in subjects aged 4 to 17 years

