#### 6.4. SIGNIFICANCE LEVEL

Unless stated otherwise, all statistical tests will be two-sided, with a significance level of 0.05. Confidence intervals (CIs) will be calculated at the 95% level, reflecting a type I error rate of 0.05.

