#### Europe:

- 1. Response at a single dose of 600 mg (1043 mg cumulative) of peanut protein: The proportion of subjects ages 4-17 who tolerate a single dose of 600 mg of peanut protein with no more than mild symptoms at the Exit DBPCFC
- 2. Response at a single dose of 300 mg (443 mg cumulative) of peanut protein: The proportion of subjects ages 4-17 who tolerate a single dose of 300 mg of peanut protein with no more than mild symptoms at the Exit DBPCFC
- 3. The maximum severity of symptoms in subjects ages 4-17 occurring at any challenge dose of peanut protein during the Exit DBPCFC
- 4. Response at a single dose of 1000 mg (2043 mg cumulative) of peanut protein: The proportion of subjects ages 18-55 who tolerate a single dose of 1000 mg of peanut protein with no more than mild symptoms at the Exit DBPCFC

Each comparison will be evaluated for statistical significance (two-sided p<0.05) only if all of the preceding tests in the hierarchy and the primary analysis of the primary endpoint are statistically significant in favor of AR101. Similar to the primary efficacy analysis of the primary endpoint, the ITT Population will be used as the primary population in pediatric subjects for analysis of key secondary endpoints as part of the hierarchical testing procedure. This closed testing procedure maintains the overall Type I error rate at 0.05 (EMEA CPMP, 2002; Cook et al., 2008). If any of the preceding tests are not significant, the p-value will be displayed for informational purposes only.

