# 9.5. ANALYSIS OF OTHER SECONDARY ENDPOINTS

If the primary efficacy analysis of the primary endpoint and all of the hierarchical testing of key efficacy secondary endpoints in pediatric subjects as described in Section 9.3 are found to be statistically significant, then statistical testing of the other secondary efficacy endpoints will continue in the order that they are listed in Section 3.2.2 according to the same hierarchical closed testing procedure used for the key efficacy secondary endpoints.

The ITT population of pediatric subjects will similarly be used for the hierarchical testing of the other secondary endpoints.

The other secondary endpoints are included in the overall hierarchical testing procedure. However, these endpoints are considered supportive in nature to the primary and key secondary endpoints. As such, no labeling claims will be made based on these endpoints if statistical significance is achieved, regardless of the success of the variables above them in the hierarchy.

Analysis of other secondary endpoints, as described below, will be performed on the pediatric subject subset (Ages 4-17) of the ITT and Completer populations. Analysis in the Completer population will not be considered for the hierarchical testing procedure.

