#### 9.5.3. Use of Epinephrine as a Rescue Medication at Exit DBPCFC

The number and percent of pediatric subjects using Epinephrine as a rescue medication at the Exit DBPCFC will be summarized by type of challenge (peanut or placebo) and treatment group. Fisher's exact test will be performed to test for a treatment difference for each type of challenge at the Exit DBPCFC.

This corresponds to the following hypotheses and the analysis at the Exit DBPCFC in pediatric subset of the Completer population will constitute the primary analysis of this secondary endpoint:

- H0: Percentage of active subjects with epinephrine use as a rescue medication at the Exit DBPCFC = percentage of placebo subjects with epinephrine use as a rescue medication at the Exit DBPCFC
- HA: Percentage of active subjects with epinephrine use as a rescue medication at the Exit DBPCFC ≠ percentage of placebo subjects with epinephrine use as a rescue medication at the Exit DBPCFC

The number and percent of pediatric subjects using Epinephrine as a rescue medication at the Exit peanut DBPCFC will be summarized by Epinephrine use at the Screening peanut DBPCFC and treatment group. A logistic regression model will be fit to assess the relationship between epinephrine use at the screening DBPCFC with epinephrine use at the

Exit DBPCFC. Epinephrine use at the Exit DBPCFC will be modelled with terms for treatment, epinephrine use at the Screening DBPCFC, and the interaction between treatment and epinephrine use at the Screening DBPCFC. The odds ratio for epinephrine use at the Exit DBPCFC with 95% CIs of the treatment effect (AR101 versus Placebo) by epinephrine use at Screening will be calculated. Similarly, the odds ratio for epinephrine use at the Exit DBPCFC with 95% CIs of epinephrine use (Yes versus No) at the Screening DBPCFC by treatment will be calculated. The score statistic will be used to calculate a p-value for each of the model terms.

Summary of epinephrine use as a rescue medication at the Exit peanut DBPCFC (yes or no) will also be summarized by each dose level (up through 1000 mg, up through 600 mg, up through 300 mg, etc.). Treatment groups will be compared using a logistic regression model with terms for treatment, epinephrine use at the Screening DBPCFC, and the interaction between treatment and epinephrine use at the Screening DBPCFC, when the dose level under examination has at least 5% of subjects with epinephrine use.

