## 9.5.6. Quality of Life Assessments

Quality of life assessment using the food allergy related quality of life questionnaire (FAQLQ), and the food allergy independent measure (FAIM) questionnaires will be performed at the Baseline and Exit visits.

Separate FAQLQ and FAIM instruments are administered based on the subject's age group. Caregiver/parent versions are also administered for subjects who are 17 years old or younger. Due to differences between the various instruments, separate summaries will be provided by age group and person who completed the questionnaire (i.e., subject or caregiver).

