## FAQLQ:

The FAQLQ is a self-report instrument that is intended to assess the effect of food allergy on the subject's quality of life. Evaluations are done by the subject (for subjects 13 years and older) and parent (for subjects 17 years and younger).

The number of items and domains varies by instrument administered. Each question is scored on a seven-point scale (van der Velde et al., 2010). The total score is the arithmetic average of all non-missing items. Domain scores are calculated similarly. The total score ranges from 1 (limited severity perception) to 7 (greatest severity perception). If less than 80% of the items are complete, then the total score will not be calculated. Similarly, if less than 80% of the items within a domain are complete, then the domain score will not be calculated.

Descriptive statistics and scores of total and domain scores along with their changes from baseline will be provided. Data will be summarized separately by age group and responder (subject or caregiver).

Analyses of change from baseline in the total and domain scores will be performed using ANCOVA models of change from baseline at the Exit visit. The model will be fit with terms for treatment group, region, and screening value. Region will be excluded from the model if any region has fewer than 3 subjects with evaluable scores within either treatment group.

Listing of the raw scores as recorded in the CRF will be provided, sorted by treatment group and subject ID.

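### The closed test sequence for the other secondary endpoints does not ensure 5% error control at the immunoglobulin and quality-of-life steps, and its epinephrine step has no eligible test

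*SAP*

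**What the plan says.** SAP 9.3 sets the rule for the key secondary endpoints: "Each comparison will be evaluated for statistical significance (two-sided p<0.05) only if all of the preceding tests in the hierarchy" and the primary analysis favour AR101. It adds: "This closed testing procedure maintains the overall Type I error rate at 0.05". SAP 9.5 applies the same procedure to the other secondary endpoints: "statistical testing of the other secondary efficacy endpoints will continue in the order that they are listed in Section 3.2.2". Under SAP 6.4, "all statistical tests will be two-sided, with a significance level of 0.05" unless stated otherwise, and SAP 6.3 allows no multiplicity adjustment beyond the hierarchy.

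The six steps, in the order of SAP 3.2.2, are:

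1. Maximum tolerated dose at the exit challenge: one Wald test (SAP 9.5.1).
2. Change in maximum tolerated dose: one ANCOVA F-test (SAP 9.5.2).
3. Epinephrine at the exit challenge: Fisher's exact test "to test for a treatment difference for each type of challenge at the Exit DBPCFC", that is, peanut and placebo (oat). SAP 9.5.3 names a primary analysis in the pediatric Completer subset but does not say which challenge it concerns.
4. Immunoglobulins: Protocol 3.7.2 lists "Changes in peanut-specific serum IgE and IgG4 levels in subjects aged 4 to 17 years". SAP 9.5.4 gives ANCOVAs for IgE, IgG4 and their ratio.
5. Skin prick test: one ANCOVA (SAP 9.5.5).
6. Quality of life: for the FAQLQ, "Analyses of change from baseline in the total and domain scores will be performed using ANCOVA models"; for the FAIM, the total score. Because the instruments differ, "separate summaries will be provided by age group and person who completed the questionnaire".

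SAP 9.5 assigns the hierarchical tests to the pediatric ITT population and excludes Completer analyses from them. It also calls these endpoints supportive and gives up labeling claims on them.

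**The concern.** A fixed sequence can spend the full 0.05 at every step because each step asks one yes-or-no question. If a step holds several tests, the plan must say which one decides, or that all must succeed, or how alpha is divided. SAP 9.5 says none of these for steps 4 and 6. The team would then have to decide, with results in hand, whether one significant immunoglobulin result passes step 4, or which questionnaire score counts at step 6.

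Step 3 has a different fault. If Completer analyses do not count in the hierarchy and the epinephrine analysis is done only in Completers, the sequence arrives at step 3 with nothing to test. Whether the immunoglobulin, skin prick and quality-of-life results are formally tested then depends on an interpretation made later.

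**Working it through.** **Inputs from the SAP.** Two-sided 0.05 per comparison (6.4, 9.3), no other adjustment (6.3), and the tests listed above. Correlations, completer numbers and epinephrine rates are not in the documents; each is marked below as assumed.

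**The plan's own figure.** With one test per step, let step j be the first whose null hypothesis is true. A false rejection anywhere requires rejecting step j, which has probability at most 0.05. The 5% in SAP 9.3 is reproduced on that condition, and steps 1, 2 and 5 meet it.

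**Several tests in a step.** If all k nulls are true, the tests are independent and any significant test counts, the error is 1 − 0.95^k. Correlated cases were simulated with normal test statistics.

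*Step 4.* Two tests: 1 − 0.95² = 9.75%. The log ratio is the difference of the two logs, so it is not a third independent test. It was simulated that way, with equal standard deviations assumed:

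| Assumed correlation, IgE and IgG4 | Two tests | With ratio |
|---|---|---|
| -0.3 | 9.5% | 10.5% |
| 0 | 9.7% | 11.5% |
| 0.3 | 9.5% | 12.1% |
| 0.5 | 9.1% | 12.2% |
| 0.8 | 7.8% | 11.8% |

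*Step 6.* The FAQLQ and FAIM are each completed by the subject (13 years and older) and by the parent (17 years and younger). Two instruments by two respondents gives at least four total scores, before any FAQLQ domain or further age form.

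- Independent: 1 − 0.95⁴ = 18.5%
- Assumed common correlation 0.5: 15.6%
- Assumed common correlation 0.9: 9.4%

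*Step 3.* Fisher's test is conservative when events are few, so its exact size was computed for two assumed completer splits (AR101/placebo). The peanut-challenge epinephrine rate was assumed to be 30% in both arms, and the two tests were combined as independent:

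| Completers | Size, peanut at 30% | Size, oat at 0.5% | Either | Size, oat at 2% | Either |
|---|---|---|---|---|---|
| 295/124 | 4.39% | 0.70% | 5.1% | 2.47% | 6.8% |
| 335/112 | 4.38% | 0.51% | 4.9% | 2.87% | 7.1% |

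For example, 1 − (1 − 0.0439)(1 − 0.0070) = 5.1%. At an assumed oat rate of 0.2% the figure is about 4.5%. Inflation here is small or absent.

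**The step 3 population.** SAP 9.5 requires ITT and excludes Completer analyses from the hierarchy. SAP 9.5.3 puts the primary epinephrine analysis, and all analyses in that section, in Completers. No epinephrine test satisfies both. Moving the test to ITT would also need a rule for subjects with no exit challenge, because SAP 7.6 imputes responder status and maximum severity but not epinephrine use.

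**The case against.** The best defence is that the wording in SAP 9.3, which opens a comparison only after all preceding tests succeed, leans towards an all-must-pass reading. On that reading no inflation carries from one step to the next. If a step were also claimed only when all its tests are significant, 5% would hold. But SAP 9.5 does not state that claim rule. Without it, single tests inside step 4 or step 6 can still be called significant at 0.05. At step 3 the same reading would probably stop the sequence: reactors to the placebo part of the screening challenge and oat-allergic subjects are excluded, so epinephrine after the oat challenge should be rare in both arms.

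It is also fair that the 5% sentence is written for the key secondary endpoints and reaches these six only by reference; that SAP 9.5.6 calls for separate summaries, so separate ANCOVAs by age group and respondent are an inference; and that a primary epinephrine analysis is named.

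A reader might infer larger errors: 9.75% at step 3, 14.3% at step 4 (three independent tests) or 26.5% at step 6 (six independent tests). The documents do not support these. The first ignores the conservatism of Fisher's test at low counts. The second treats a ratio as independent of its own components, and the ratio is not among the endpoints listed in SAP 3.2.2. The third needs six tests, and the SAP does not give the number of questionnaire forms or domains.

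**Conclusion.** The point stands in limited form. As written, SAP 9.5 does not ensure 5% control at steps 4 and 6. Under an any-significant-test rule, the error is about 8–10% for the two listed immunoglobulin endpoints and 10.5–12% with the ratio, at assumed correlations of -0.3 to 0.8. For four quality-of-life totals it is 18.5% if independent and about 9% at an assumed correlation of 0.9. Each figure takes all nulls in the step to be true; domain scores would raise the last pair. At step 3 the inflation is slight (about 4.5–7% under assumed rates). The real fault there is that no test is eligible, so the route to steps 4–6 is undefined.

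A reader might go further and conclude that the 5% statement is false or that the main efficacy conclusions are exposed. Neither follows. An all-tests claim rule would restore 5%, so control is not ensured rather than shown to fail. The primary and key secondary tests come earlier in the sequence and are untouched. With no labeling claims on these endpoints, what is at stake is which results the study report may call significant within the hierarchy.

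**What to change.** Amend SAP 9.5 before unblinding:

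- Name one confirmatory test per step, or give an explicit one-at-a-time order, as SAP 9.4 already does for symptom severity at successive challenge doses. For example: epinephrine at the peanut challenge; peanut-specific IgE, then IgG4, in the SAP 3.2.2 order, with the ratio nominal; skin prick test; one prespecified FAQLQ total; then one FAIM total. State the form and respondent for both questionnaires.
- Alternatively, use Holm within a step and open the next step only if all tests in that step succeed. The smallest p-value would then face 0.025 with two tests and 0.0125 with four.
- Reconcile SAP 9.5 with SAP 9.5.3 on the population for the epinephrine test. Choosing the peanut challenge alone does not settle this. Either admit the Completer analysis as a stated exception, or define an ITT test with a rule for subjects who have no exit challenge.
- Label every other test in these sections nominal.

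The cost is a few lines of SAP text, and some comparisons become descriptive. SAP 1.1 says the staff developing the SAP remain blinded until after database lock, so the choice can still be made without knowledge of results.

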#### 9.5.1. Maximum Tolerated Dose at Screening and Exit DBPCFCs

The Screening and Exit DBPCFCs are based on a modified PRACTALL dosing regimen as described in section 2.7 (see Table 2.4). With the exception of the 600 mg dose, the modified PRACTALL doses are approximately on a logarithmic scale.

Estimates for the probability of tolerating each challenge dose or higher in the Exit DBPCFC will be based on the discrete hazards model with terms for treatment group effect, region (NA, EU), and the MTD at the Screening DBPCFC (baseline) in the log10 scale (Chinchilli et al., 2005). Following Chinchilli, the extreme value hazard function will be used for the discrete-time hazard function and the model will be fit with logistic regression with the complementary log-log link function. Subjects with no dose eliciting response at the 1000 mg single dose will be censored at that dose.

The probability estimates for each dose level will be tabulated by treatment group based on LS Mean estimates from the above model (i.e., adjusted for the MTD at baseline and region). The adjusted probability estimates will also be plotted. An unadjusted probability estimate will also be calculated by removing the MTD at baseline and region terms from the model. All subjects in the analysis population are considered eligible for the 1 mg dose. If the optional 1 mg dose was not taken, the subject is considered to have passed it.

The treatment group effect will be assessed using the model with terms to adjust for the MTD at baseline and region. The hazard ratio for the treatment group effect with its 95% confidence interval and the p-value will be based on the Wald statistic. If a subject did not participate in the Exit DBPCFC, the screening results will be used.

The hazard ratio is an estimate of the ratio of the conditional probability of not tolerating a single dose of the DBPCFC given the subject tolerated the lower doses for AR101 subjects relative to Placebo subjects. The comparison of treatment groups using the discrete hazards model corresponds to the following hypothesis:

- $H_0$ : The hazard ratio for subjects within active subjects relative to placebo subjects = 1 when controlling for baseline MTD and region
- $H_A$ : The hazard ratio for subjects within active subjects relative to placebo subjects  $\neq$  when controlling for baseline MTD and region

The proportional hazard model assumption for treatment effect will be checked graphically with a log-log plot of Kaplan-Meier estimates for each treatment arm by dose level. Overall validity of model assumptions will be checked by visual comparison of Kaplan-Meier estimates with estimates from the unadjusted and adjusted models.

The peanut MTD at Screening and Exit DBPCFCs will be listed. Imputed peanut MTD at the Exit DBPCFC will be flagged.

Analyses will be performed in the ITT and Completer populations.

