In ARC001, 56 subjects were randomized: 29 subjects to AR101 and 27 subjects to placebo. Consent for 1 subject was withdrawn after the subject was randomized, but before the first dose of study treatment was administered. The intent-to-treat (ITT) population, thus, comprised 55 subjects in total, 29 in the AR101 and 26 in the placebo arm. The 2 study groups were overall well matched for baseline characteristics including baseline sensitivity in the Screening DBPCFC. Six subjects in the AR101 arm withdrew from the study prior to the Exit DBPCFC.

For the primary efficacy analysis conducted in the ITT Population, AR101 was shown to be statistically significantly superior to placebo, with 23 of 29 (79%) AR101 desensitization responders as compared to 5 of 26 (19%) placebo desensitization responders, resulting in a treatment difference of 60% (p < 0.0001 by Fisher's exact test).

At the time of the Exit DBPCFC, 100% of the 23 AR101 subjects undergoing the DBPCFC (Completer Population) tolerated 300 mg as compared to, 5 of the 26 (19%) placebo study completers, resulting in a treatment difference of 81% (p < 0.0001 by Fisher's exact test).

It was also found at Exit DBPCFC that 18 of 29 (62%) AR101 subjects in the ITT Population tolerated 600 mg while none of placebo subjects tolerated 600 mg, resulting in a treatment difference of 62%. Post-hoc analysis by Fisher's exact test yielded statistical significance at the p < 0.0001 level. In the Completer Population, 18 of 23 (78%) AR101-treated subjects and no placebo subjects tolerated 600 mg at Exit DBPCFC.

For the key secondary endpoint of the maximum dose achieved with no or mild symptoms at the Exit DBPCFC, analyzed using a discrete hazard model, AR101 treatment was shown to increase the probability of tolerating higher maximum doses with no or mild symptoms as compared with placebo treatment. The adjusted probability of tolerating 300 mg was 0.82 for AR101 and 0.14 for placebo; the adjusted probability of tolerating 600 mg was 0.59 for AR101 and 0.01 for placebo. Overall, the treatment effect hazard ratio (95% CI) was determined to be 0.10 (0.04, 0.25) (p < 0.0001), indicating that the risk of failing the Exit DBPCFC in AR101 subjects was one-tenth the risk as compared to placebo subjects.

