9.2.2.2 Analysis of Other Selected Secondary Endpoints

- Maximum dose achieved with no or mild symptoms at Exit DBPCFC: The probability estimates for tolerating each challenge dose or higher of the Exit DBPCFC will be calculated based on the discrete hazards model in the ITT population with terms for treatment group effect, region (North America and Europe) and the MTD at the Screening DBPCFC (baseline) in the log₁₀ scale (Chinchilli et al., 2005). The extreme value hazard function will be used for the model. The probability estimates will be tabulated by treatment group and adjusted for their Screening MTD. The values for MTD for subjects who do not undergo the Exit DBPCFC will be imputed using the maximum doses of peanut protein tolerated in their Screening DBPCFC. The treatment effect hazard ratio and its 95% confidence interval (95% CI) and p-value will be based on the Wald statistic.
- Change from baseline in maximum tolerated dose (MTD) of peanut protein at DBPCFC: Analyses of change from baseline MTD will be performed using change calculated on the log₁₀ scale. An analysis of covariance (ANCOVA) model of change from baseline MTD at Exit DBPCFC (log₁₀ mg) will be fit with terms for treatment group, region, and the MTD at baseline (log₁₀ mg). The values for MTD for subjects who do not undergo the Exit DBPCFC will be imputed using the maximum doses of peanut protein tolerated in their Screening DBPCFC. The baseline adjusted least squares means with 95% CIs by treatment group and for the treatment group difference will be tabulated. The p-value is based on the F-test for treatment group effect adjusted for the MTD at baseline (log₁₀ mg). Residuals for ANCOVA will be assessed for non-normality using the Shapiro-Wilk test. If significant at the 0.05 level, then the Wilcoxon rank sum statistic will be used to test for a treatment group difference to examine the robustness of the ANCOVA F-test.

The statistical methods used for testing the remaining secondary endpoints are described in the Statistical Analysis Plan (SAP).

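### SAP 9.5.1 describes the discrete-hazards hazard ratio as a ratio of conditional failure probabilities, which its complementary log-log model does not estimate; read as a risk ratio it looks too favourable

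*SAP*

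**What the plan says.** SAP 9.5.1 models the highest dose tolerated at the Exit DBPCFC with terms for treatment, region and screening MTD, and states that "the model will be fit with logistic regression with the complementary log-log link function". Protocol 9.2.2.2 names the same model: "The extreme value hazard function will be used for the model". SAP 9.5.1 then explains the treatment estimate: "The hazard ratio is an estimate of the ratio of the conditional probability of not tolerating a single dose of the DBPCFC". It conditions this on lower doses having been tolerated and sets AR101 against placebo. The null hypothesis is a hazard ratio of 1, tested with a Wald statistic. Adjusted and unadjusted probabilities of tolerating each dose are to be tabulated by arm.

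Protocol 1.2.2.1 reports the Phase 2 endpoint, "analyzed using a discrete hazard model". The hazard ratio was 0.10 (95% CI 0.04 to 0.25), interpreted as "indicating that the risk of failing the Exit DBPCFC in AR101 subjects was one-tenth the risk as compared to placebo subjects". The same paragraph gives the fitted probabilities: "The adjusted probability of tolerating 300 mg was 0.82 for AR101 and 0.14 for placebo". At 600 mg the corresponding figures are 0.59 and 0.01.

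Under SAP 9.5 this is the first of the other secondary endpoints in the testing order. They are described as supportive, with no labelling claim to rest on them.

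**The concern.** The model and the sentence that explains it disagree. With a complementary log-log link, the exponentiated treatment coefficient is a ratio of -ln(1 - h). This is close to a ratio of the h values when both are small. In a food challenge that runs to 1000 mg they are not small, because at the upper doses most placebo subjects who are still being challenged are expected to fail.

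A report that follows the SAP sentence would present the hazard ratio as a relative risk of failing a dose, and the ratio would look more favourable than the failure probabilities from the same fitted model. Protocol 1.2.2.1 already reads the Phase 2 result this way. SAP 9.6.5 uses the same type of model, with hazard ratios for each baseline factor, so the misreading could carry into those tables too.

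**Working it through.** **Inputs.** From Protocol 1.2.2.1 (ARC001): adjusted probability of tolerating 300 mg, 0.82 on AR101 and 0.14 on placebo; of tolerating 600 mg, 0.59 and 0.01; hazard ratio 0.10. ITT counts: 23 of 29 v 5 of 26 tolerated 300 mg, and 18 of 29 v 0 of 26 tolerated 600 mg. From Protocol 9.4 (ARC003 planning): 50% v 20% at 600 mg and 30% v 15% at 1000 mg. Assumption: ARC001 used the same link as ARC003. The protocol does not state it.

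**What the link gives.** With ln(-ln(1 - h)) linear in treatment, HR = ln(1 - h_A)/ln(1 - h_P) at every dose step. Multiplying over steps, S_A = S_P^HR, where S is the probability of tolerating a dose or higher. Hence HR = ln S_A / ln S_P.

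**Reproducing the reported 0.10.**
- 300 mg: ln 0.82 / ln 0.14 = 0.101 (0.096 to 0.106 over rounding of the inputs).
- 600 mg: ln 0.59 / ln 0.01 = 0.115 (0.098 to 0.128).

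Both agree with 0.10 within rounding, so the reported figure behaves as a ratio of logs.

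**The quantity the SAP sentence describes, for 600 mg given 300 mg tolerated.**
- AR101: 1 - 0.59/0.82 = 0.280.
- Placebo: 1 - 0.01/0.14 = 0.929.
- Ratio: 0.280/0.929 = 0.30 (0.28 to 0.33 over rounding).

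Had 0.10 been this ratio, AR101 conditional failure would be 0.10 × 0.929 = 0.093, and the probability of tolerating 600 mg would be 0.82 × (1 - 0.093) = 0.74. The protocol gives 0.59.

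**Cumulative failure.**
- By 300 mg: 0.18/0.86 = 0.21.
- By 600 mg: 0.41/0.99 = 0.41.

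**Crude ITT counts, which need no link assumption.**
- Failing 300 mg: (6/29)/(21/26) = 0.26.
- Failing 600 mg: (11/29)/(26/26) = 0.38.

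Neither is near one-tenth.

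**Size as a risk reduction.** A risk ratio of 0.10 means a 90% reduction.

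| Measure (ARC001, adjusted) | Ratio | Reduction | 90% divided by reduction |
|---|---|---|---|
| Cumulative, by 300 mg | 0.21 | 79% | 1.1 |
| Conditional, 600 mg given 300 mg | 0.30 | 70% | 1.3 |
| Cumulative, by 600 mg | 0.41 | 59% | 1.5 |

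**Where the approximation breaks down.** With HR = 0.10, the conditional-probability ratio is [1 - (1 - h_P)^0.1]/h_P. This gives 0.105, 0.117, 0.134, 0.186 and 0.229 at h_P = 0.1, 0.3, 0.5, 0.8 and 0.9. The SAP sentence is a fair approximation at steps with low placebo failure and a poor one at steps with high placebo failure.

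**At ARC003's planning rates.**
- 600 mg: implied HR = ln 0.50/ln 0.20 = 0.43; failure ratio = 0.50/0.80 = 0.63.
- 1000 mg: implied HR = ln 0.30/ln 0.15 = 0.63; failure ratio = 0.70/0.85 = 0.82.

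Read as risk ratios, these hazard ratios would claim reductions of 57% and 37%, where the planning rates give 38% and 18%.

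**The case against.** The strongest reply is that nothing inferential depends on the sentence. HR = 1 exactly when the conditional probabilities are equal, so the hypotheses, Wald p-value, testing order and fitted probabilities all stand. SAP 9.5.1 checks proportional hazards with a log-log plot, which is the right check for this model, and SAP 9.5 rules out labelling claims. All of that stands. It limits the consequence, but it does not make the definition correct.

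A reader might infer from 0.30 against 0.10 that the risk reduction is overstated threefold. The documents do not support that. Threefold is the quotient of two ratios at one dose step with very high placebo failure, and it rests on a placebo probability printed as 0.01. As a risk reduction, that step compares 90% with about 70%.

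A reader might also infer that the hazard ratio is the only effect estimate planned for tolerated dose. It is the only between-arm measure with a confidence interval within SAP 9.5.1. But SAP 9.1 and 9.3.1 plan response-rate differences with 95% confidence intervals at 300, 600 and 1000 mg, and SAP 9.5.2 plans an ANCOVA of change in MTD with geometric mean ratios.

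Two further points stand. The ARC001 link is inferred from the fit of the numbers, although the crude counts contradict the one-tenth reading without it. And a conditional ratio at 600 mg compares those who tolerated 300 mg (about 82% of AR101 and 14% of placebo on the ARC001 figures), which is not a randomised comparison and should not become the preferred risk measure.

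**Conclusion.** The SAP sentence is wrong as a definition for the model specified: the hazard ratio is a ratio of -ln(1 - h), and it approximates a ratio of conditional probabilities only where few subjects fail. On the ARC001 adjusted figures, treating 0.10 as a risk ratio overstates the relative risk reduction by 1.1- to 1.5-fold (90% against 59% to 79%), assuming the same link and fitted probabilities evaluated at common covariate values. The statement in Protocol 1.2.2.1 has the same fault, and the crude failure ratios of 0.26 and 0.38 contradict it directly. This is an error of interpretation in a supportive endpoint. It does not invalidate the model, its test or the testing sequence.

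**What to change.** Keep the model and its test. Replace the explanatory sentence in SAP 9.5.1 with: *The hazard ratio is the AR101:placebo ratio of -log(1 - conditional probability of not tolerating a dose); it is not a risk ratio.* Base any statement about risk on the by-arm tolerance probabilities already tabulated in 9.5.1, showing their complements (cumulative probability of not tolerating 300, 600 and 1000 mg), and on the response-rate differences with confidence intervals already planned. Apply the same reading to the hazard ratios in SAP 9.6.5. Correct the one-tenth statement in Protocol 1.2.2.1. Conditional ratios by dose with delta-method or bootstrap intervals are optional: they partly duplicate planned output and are not randomised comparisons.

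The cost is one SAP sentence, a few columns in an existing table and one protocol sentence. No p-value changes. The downside for the sponsor is that the effect, as described, becomes less favourable.
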